#### **B2. Clinical Studies Overview**

As the only parenteral non-selective NSAID available in the United States, ketorolac has been evaluated frequently (36). Glassman found a more than fourfold higher proportion of pseudoarthrosis in patients receiving ketorolac than those that did not. In the Glassman study, the overall incidence of nonunion was 11.8% in 288 patients (48.9% of the study population were smokers). Their work was the first clinical trial to propose that NSAIDs, and ketorolac specifically, may delay bone healing

following spinal fusion (37).

Critics of the Glassman paper have cited that smokers made up 48.9% of the study population and thus the difference observed was either due to effect modification with the synergistic detriments of ketorolac and smoking resulting in the observed significant difference of 13.3% between the experimental and control arms. If the observations were limited to non-smokers, the overall incidence drops to 6.8% and the difference between treatment arms becomes 8.9%. This represents an overall reduction of nonunions by 43% and a halving of the difference between ketorolac and controls (37).

Pradhan and associates conducted a study in a similar population as Glassman's but excluded smokers. Of the 405 patients undergoing spinal fusion, Pradhan noted a 0.9% higher rate of pseudoarthrosis in patients without ketorolac versus those who did receive the drug with an overall incidence in 5.67% in a population of non-smokers. They concluded that ketorolac does not negatively impact bone healing. Pradhan's spinal nonunion incidence among nonsmokers of 5.6% does seem to be more consistent with the non-smoking Glassman patients of 6.8%. However, a substantial limitation of this study was that patients in both treatment arms could have received autogenous bone graft. (38).

A 2005 article of 434 subjects compared patients taking no NSAIDs versus ketorolac undergoing spinal fusion with an overall incidence of 11.1%, and 2.6% among non-smokers. Smokers contributed 3.6% of the total population and were relatively balanced in the groups. Among non-smokers, ketorolac users had a 3.4% and controls had a 2.2% nonunion rate. In this same experiment Rofecoxib and Celecoxib were also tested and had a 2.2% and 2.3% respective nonunion rate among non-smokers. Thus they noted that ketorolac may have the potential to inhibit bone healing (39).

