Finally, Sucato noted a 1.2% ( $p>0.05$ ) difference in the proportion of patients taking no NSAIDs versus ketorolac undergoing spinal fusion with an overall incidence of 2.5%. Smokers made up 0.6% of the study population and none of them developed a nonunion. Among non-smokers, 1.9% Ketorolac users and 3.1% of controls had a nonunion ( $p>0.05$ ). The overall incidence among non-smokers was 2.5% (40).

To the authors' knowledge, only retrospective reviews evaluating the influence of ketorolac and delayed healing have been conducted in the clinical setting. As noted above, this includes both supportive and antagonistic evidence. Furthermore, ketorolac, as well as other NSAIDs have been primarily studied in spine surgery or studies dealing with traumas and high energy fractures. In all of the studies evaluating NSAIDs and post-operative bunionectomy pain, bone healing was not evaluated, nor reported as a significant adverse event. This is an important distinction to note, since bunion correction involves long bone healing while spinal surgery entails irregular bone healing. Bunionectomy procedures also involve making a controlled osteotomy cut which may biologically vary substantially from traumatic and fusion of two independent bones as is the case with spine arthrodesis.

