Nonunion was defined as grades 4 or 5. Nonunion analysis was performed by two independent foot and ankle surgeons. Both evaluators agreed that there was one nonunion out of 29 cases or 3.45%. This compares favorably with historical controls. According to prior literature, baseline nonunion rates (traditional Lapidus approach, no ketorolac reportedly given) for this procedure ranges between 0-12%, with higher nonunion rates occurring in older literature. It is believed that nonunion rates were higher in older literature due to the use of smaller screw sizes and antiquated surgical techniques (42-50). This pilot data implies that the addition of ketorolac did not appear to have adverse consequences with bone healing in this cohort of patients.

[figure not shown]

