The next consideration for study design is the sample size calculations for delayed and nonunion in each group. Because earlier calculations have already incorporated ICC assumptions, the previous approach is still considered appropriate. Again drawing from higher level studies, the difference to detect has been determined to be 20.5% between groups (38). Using the same criteria from the previous calculations, an 80% power to detect differences between groups with a 0.05 two-sided significance will require a total sample size of 76, or 38 subjects per arm. If the ICC were to be changed to 0.01 detection of a 20.5% difference requires 40 patients per group with five clusters of sixteen patients for the total of 80 subjects. Given the ICC assumptions of the VAS calculations the authors have already attempted to incorporate a highly conservative sample calculation and included a 10% inflation for drop-outs.

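### The bone-healing sample size rests on a 20.5-point difference that the protocol's own account of the cited study does not contain, and no control rate is given, so calling 88 patients adequate for that aim is unsupported

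*Combined protocol and SAP*

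**What the plan says.** All figures are in the combined protocol and SAP.

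- **Bone-healing size** (B3.B, a. Sample Size Justification). For delayed union and nonunion, "the difference to detect has been determined to be 20.5% between groups (38"). At 80% power and two-sided 0.05 this is said to need 76 patients, 38 per arm. With an ICC of 0.01 the same difference "requires 40 patients per group with five clusters of sixteen patients for the total of 80 subjects". Neither arm's event rate is given, and no formula is named.
- **Reference 38 as the protocol describes it** (Background, B2. Clinical Studies Overview): "a 0.9% higher rate of pseudoarthrosis in patients without ketorolac versus those who did receive the drug with an overall incidence in 5.67"%.
- **Other ketorolac-control differences in that overview, all in spinal fusion.** Reference 37: "the observed significant difference of 13.3% between the experimental and control arms", and among non-smokers "the difference between treatment arms becomes 8.9"%. Reference 39, non-smokers: "ketorolac users had a 3.4% and controls had a 2.2% nonunion rate". Reference 40, non-smokers: "1.9% Ketorolac users and 3.1% of controls had a nonunion".
- **Bunionectomy background** (C. Preliminary Studies/Pilot Data): "baseline nonunion rates (traditional Lapidus approach, no ketorolac reportedly given) for this procedure ranges between 0-12"%. The pilot found 1 nonunion in 29 Lapidus patients given ketorolac (3.45%). Neither figure is linked to the sample size.
- **Conclusion of the justification.** 80 patients plus 10% gives 88 (44 per arm), and 88 is declared adequate for the study's aims with no restriction to pain.
- **Pain calculation, same section.** The main run assumes an ICC of 0.08 or more and needs 40 per arm for a 1.3 VAS difference. A sensitivity run, described as using a non-contributory ICC and also printed as 0.08, needs 20 per arm for the smallest clinically significant difference. No SD is stated.

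**The concern.** A two-proportion sample size is fixed by the difference, the control rate, alpha and power. Here the difference is credited to a study that the protocol itself summarises as 0.9 points in the opposite direction, and the control rate is missing. A reader cannot tell where 20.5% came from or whether 38 follows from it.

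Possible harm to bone healing is the reservation about ketorolac that the background sets out at length, and Possible Benefits says the results will be strong evidence for one side or the other. If the adequacy statement stands, a non-significant delayed-union result could be taken as coming from a comparison that was properly sized to find harm. The documents do not show that it was.

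**Working it through.** **Inputs.** Difference d = 0.205, two-sided alpha 0.05, power 80%, 38 per arm stated, 44 per arm planned (all Sample Size Justification). The control rate p1 is not given, so it is varied over values printed elsewhere: 2.2% and 3.1% (non-smoker controls, references 39 and 40), 3.45% (pilot), 5.67% (reference 38 overall) and 12% (top of the Lapidus range). These are assumptions: they come from other operations or from nonunion, not from 12-week delayed union after a Kalish procedure.

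**Step 1: can 38 per arm be reproduced?** Pooled normal formula, with p2 = p1 + d and pbar = (p1 + p2)/2:

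n = [1.96 √(2 pbar(1 − pbar)) + 0.8416 √(p1(1 − p1) + p2(1 − p2))]² / d²

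- p1 = 1.5%: p2 = 22.0%, pbar = 11.75%; (0.8926 + 0.3633)² / 0.042025 = 37.5, so 38.
- p1 = 5.67%: p2 = 26.17%, pbar = 15.92%; (1.0141 + 0.4180)² / 0.042025 = 48.8, so 49.

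| Assumed control rate | n per arm for 20.5 points |
|---|---|
| 0% | 34 |
| 1.5% | 38 |
| 2.2% | 40 |
| 3.45% | 43 |
| 5.67% | 49 |
| 12% | 64 |

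The arcsine formula gives 37.3, so 38, at the 3.45% pilot rate. The figure of 38 is therefore reachable, but only by supplying a rate and a formula that the plan does not state.

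**Step 2: power at 44 per arm for 20.5 points.** At 5.67%, z = (0.205 × √44 − 1.0141) / 0.4967 = (1.3598 − 1.0141) / 0.4967 = 0.696, so power is about 76%. Exact enumeration with Fisher's test gives 69%. At 2.2% the two figures are 84% and 81%; at 12% they are 64% and 55%.

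**Step 3: power at 44 per arm for differences the protocol prints** (Fisher exact, before losses):

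| Difference | Control 2.2% | Control 5.67% | Control 12% |
|---|---|---|---|
| 20.5 points (justification) | 81% | 69% | 55% |
| 13.3 points (reference 37) | 45% | 37% | 26% |
| 8.9 points (reference 37, non-smokers) | 19% | 17% | 13% |

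Fisher is used because Secondary Outcomes names it for binary data. The bone-healing analysis itself is planned as logistic regression, so these figures are illustrative.

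**Step 4: the pain ICC.** The main run has ICC at least 0.08, a 1.3 difference and 40 per arm. The sensitivity run has ICC 0.08, the smallest clinically significant difference (also 1.3) and 20 per arm. If both used 0.08 with the other inputs unchanged, the sizes could not differ by 40/20 = 2. The value printed for the sensitivity run also clashes with its description as non-contributory.

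**The case against.** **A design difference need not equal an observed one, and reference 38 may contain 20.5% somewhere.** Both are true, and the paper cannot be checked from the documents. But the justification presents the figure as drawn from that study and gives no other rationale, and the protocol's own summary of the study does not contain it. The mismatch inside the document stands.

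**The number 38 may be right.** This also stands. Step 1 reaches 38 by two standard formulas at low control rates. A reader might infer an arithmetic error; the documents do not show one.

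**Low power is not shown.** Correct. At a 2.2% control rate, 44 per arm gives more than 80% power for 20.5 points. The smaller differences come from spinal fusion, the larger one from a cohort with 48.9% smokers, and the background says that bunion osteotomy may heal differently. A reader might infer that the trial is underpowered for bone healing; that needs a control rate and a target difference that nobody has stated.

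**The ICC 0.01 step.** It is tempting to compute 1 + 15 × 0.01 = 1.15 and 38 × 1.15 = 43.7, and to say that the printed 40 is wrong. That does not hold. The text does not say that 38 was free of ICC inflation, the multiplier is for whole clusters assigned to one arm, patients are randomised individually, and five clusters cannot divide evenly between two arms.

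**The plan partly protects itself.** Odds ratios with 95% confidence intervals are already planned for delayed union and nonunion, and no absence-of-harm conclusion is promised. This lowers the severity but does not support the adequacy statement.

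**The pain ICC.** The main run says at least 0.08, so a larger value may have been used there. A misprint in the sensitivity run is the most natural explanation, and the plan adopts the larger size in any case.

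**Conclusion.** The concern holds in limited form. The 20.5-point basis conflicts with the protocol's own account of reference 38 (0.9 points, higher without ketorolac) and exceeds every ketorolac-control difference it prints, the largest being 13.3. Without a control rate or formula, 38 per arm cannot be verified: the pooled formula gives 34 to 64 per arm over control rates of 0 to 12%. The statement that 88 is adequate for the study aims is therefore unsupported for bone healing. Neither an error in 38 nor low power has been demonstrated.

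Separately, the ICC printed for the pain sensitivity run appears to be wrong, and the missing SD prevents a check.

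The sizes quoted rest on borrowed control rates, 44 evaluable patients per arm and no clustering. Missing Data counts patients lost from longer follow-up as treatment failures, which would change the event rates. Pain is the primary outcome and its size of 80 before inflation is unaffected, so this should be fixed rather than being critical.

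**What to change.** Keep N at 88 and change the wording in three places.

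1. **Bone-healing paragraph of the Sample Size Justification.** Correct or remove the 20.5% basis credited to reference 38, or state a sourced difference with its control rate, formula and ICC, and recompute the size.
2. **Adequacy statement.** Limit it to pain. Add that p > 0.05 for delayed union will not be read as absence of harm, and that the between-group risk difference will be reported with its 95% CI beside the planned odds ratio. If power is printed, compute it for the test actually planned over stated non-zero control rates. For example, Fisher exact at 44 per arm and control rates of 2.2 to 12%, before losses, gives about 55-81% for 20.5 points, 26-45% for 13.3 and 13-19% for 8.9.
3. **Pain paragraph.** Correct the ICC of the sensitivity run and state the SD used.

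The cost is protocol and SAP text, plus one added summary of data already collected. There are no extra patients or visits. The drawback is that the stated power for bone healing becomes less favourable.

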**Thus, the previously noted 88 total sample size (44 patients per treatment arm) was estimated to**

**be adequate to achieve study aims and goals.**

**b. Data Analysis**

**Outcomes and their Measurements**

*a. Primary Outcome*

All analyses will be calculated using Statistical Analysis Software (SAS, Worldwide Headquarters, Cary, NC) and will be based on the **intention-to-treat principle**.

The primary outcome of interest is pain measured on the second post-operative day, 48 hours ( $\pm 4$  hours) following surgery. This will allow the effects of anesthesia to subside following surgery. This will be well within the five day window in which the patient will be taking ketorolac post-operatively.

Pain will be measured by both unidimensional and multidimensional instruments. A blinded trained research fellow will contact patients by telephone and will administer the McGill Pain Questionnaire-Short Form (MPQ-SF) and instruct patients to fill out the visual analog scale (VAS). This will occur 48 hours ( $\pm 4$  hours) post-operatively. The VAS will be pre-printed in a diary that is given to the patient post-operatively. The VAS will be 10 cm in length with the end anchors, "no pain" and "worst pain possible". If patient compliance with the VAS is greater than 95%, then the VAS will be used for the primary analysis. As a back-up, the MPQ-SF will be utilized as the primary analysis. Regardless, sensitivity analyses will be conducted to verify the robustness of the results. The research fellow will also obtain the patient's post-operative pain medication consumption (including timing and dosages) and verbally confirm study protocol compliance during this telephone interview (Please refer to the variables collected section for full details; A telephone script is also included in this IRB application). Regression will be utilized to control for measured confounders, including timing of the telephone interview and last dose of post-operative pain medication. Standard regression model rules will be applied and a p-value  $\leq 0.05$  will be considered statistically significant in the final regression model.

The patient diaries with the VAS will be collected during the first post-operative visit (one week). Patients will be asked to bring all surgery related medications and bottles to this post-operative appointment. The research fellow will again obtain the patient's post-operative pain medication consumption (including timing and dosages) by counting pills and verbally confirm study protocol compliance (Please refer to the variables collected section for full details).

Whether a difference in delayed unions at twelve weeks exists between the two groups will also be assessed. Radiographic union for each patient will be assessed by both a blinded, board-certified radiologist and two blinded board-certified podiatric surgeons. Agreement between these three experts will be assessed with a kappa score and the mean result will be used for primary analysis. Delayed and non-union rates will be compared between the two groups. A previously documented scoring system found to have both high inter- and intra-observer reliability in a series of tibial fractures reduced surgically will be utilized for this assessment. This scoring system grades each fracture according to four characteristics: 1. Rating of fracture healing, 2. Callus morphology, 3. Number of cortices visible or obliterated. 4. Number of cortices bridged (41). The modification utilized for this study will be as follows:

- ❖ **Grade 1:** Homogenous bone structure with complete obliteration of fusion site
- ❖ **Grade 2:** Massive bone trabeculae crossing fusion site, 3-4 cortices are bridged with fusion site barely discernable
- ❖ **Grade 3:** Apparent bone trabeculae crossing fusion site, 2-3 cortices are bridged with fusion site discernable
- ❖ **Grade 4:** Trace bone trabeculae crossing fusion site, 1-2 cortices are bridged with distinct visible joint space

- ❖ **Grade 5:** No bone trabeculae crossing fusion site, 0 cortices are bridged with complete visible joint space

A delayed-union will be defined as a grade 4 or 5 in any patient over twelve weeks. A nonunion will be defined as a grade 4 or 5 in any patient over six months. Analysis will include logistic regression for these binary endpoints. Odds ratios and 95% confidence intervals will be calculated between groups (delayed and/or non-union: yes/no). A 2-sided p value of  $\leq 0.05$  will be considered statistically significant.

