### **B. Statistical Considerations**

#### **a. Sample Size Justification:**

In performing the required sample size calculations, the authors assumed that potential cluster effects may be evident as a function of the individual surgeon. Because of this likelihood of cluster effects, we estimate the power of the study for change in post-operative pain that assumes an intra-class correlation (ICC) of at least 0.08 to inflate sample size estimates. This assumes 80% power to detect differences between groups with a 0.05 two-sided significance. Previous literature reports that in comparisons of opioid alone versus ketorolac with opioid the mean difference was observed to be 1.8 on the VAS (16). The widely accepted minimum clinically significant pain relief has been reported to be 1.3 (17). Detection of a 1.3 absolute difference in change in pain relief between groups requires 40 patients per group; detection of a 1.8 difference requires 20 patients per group consisting of eight and four (surgeons) respectively, assuming clusters of 10 subjects each. These calculations use an extremely high ICC which maximizes its accuracy. Because of the unknown ICC influence, a sensitivity analysis was performed assuming a non-contributory ICC of 0.08 which required a total sample size of 20 subjects per arm using the smallest clinically significant difference to detect.

Based on these calculations the largest sample required is 80 subjects. In order to preserve statistical power in the face of drop-outs and patient contact difficulties, the total sample size will be inflated by 10% such that the final projected sample size will be 88 subjects, or 44 per arm.

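### The primary pain scale switches from the VAS to an unsized MPQ-SF at an undefined 95% compliance; counted over all 88 randomized, this can happen with the required 80 VAS scores in hand

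*Combined protocol and SAP*

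**What the plan says.** The rule appears twice, in section B3 A.4 (Day Two) and under Primary Outcome in Data Analysis: "If patient compliance with the VAS is greater than 95%, then the VAS will be used for the primary analysis". The next sentence in both places is "As a back-up, the MPQ-SF will be utilized as the primary analysis". The Primary Outcome text adds "Regardless, sensitivity analyses will be conducted to verify the robustness of the results", without naming any such analysis. It also plans an adjusted model: "Regression will be utilized to control for measured confounders, including timing of the telephone interview and last dose of post-operative pain medication".

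The VAS is a 10 cm line in a paper diary. The patient marks it after instruction on the 48-hour call, and the diary is collected at the week-one visit. The MPQ-SF is administered live on the same call. Both scales are also recorded on Day 0.

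The Sample Size Justification uses VAS differences: "Detection of a 1.3 absolute difference in change in pain relief between groups requires 40 patients per group". A difference of 1.8 needs 20 per group. It concludes "Based on these calculations the largest sample required is 80 subjects" and then adds a reserve: "In order to preserve statistical power in the face of drop-outs and patient contact difficulties, the total sample size will be inflated by 10" per cent, giving 88, or 44 per arm.

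The Missing Data section counts lost patients as failures only for outcomes with longer follow-up. It promises unspecified sensitivity analyses for anything else.

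**The concern.** The rule and the sample size set different tolerances for loss. The sample size allows for losing 8 of 88 patients. The scale rule, if counted over everyone randomized, allows 4. Between those limits the plan would stop treating as primary the only pain scale it was sized on, at a level of loss it has budgeted for.

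The replacement is not fully specified. The MPQ-SF appears as an instrument to administer and as a literature reference, but no score, relevant difference or power is given. Because compliance is undefined, the same 80 returned forms can lead to either scale being primary. At stake is which result is reported as the primary one, and whether that result has a stated target difference behind it.

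**Working it through.** **Inputs.** From the Sample Size Justification: 80 subjects required, 10% inflation, 80% power, two-sided 0.05, ICC 0.08, clusters of 10, differences of 1.3 (40 per group) and 1.8 (20 per group). From Primary Outcome: a threshold strictly above 95%. The VAS non-completion rate is not in the documents, so a range is assumed.

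**1. The plan's own figure.** 80 × 1.10 = 88. Reproduced. The budgeted loss is 8/88 = 9.1%.

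**2. Threshold over all 88.** 0.95 × 88 = 83.6, so at least 84 forms are needed: 84/88 = 95.5% passes and 83/88 = 94.3% fails. 80/88 = 90.9% also fails. With 80, 81, 82 or 83 forms the requirement of 80 is met but the MPQ-SF is primary.

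**3. Threshold over patients reached.**

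| Patients counted | Fewest forms that keep the VAS | Counts of 80 or more that lose it |
|---|---|---|
| 84 | 80 (95.2%) | none |
| 85 | 81 (95.3%) | 80 |
| 86 | 82 (95.3%) | 80–81 |
| 87 | 83 (95.4%) | 80–82 |
| 88 | 84 (95.5%) | 80–83 |

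With 80 to 84 patients counted, 80 forms always keep the VAS (100% down to 95.2%). The conflict narrows as the denominator falls and is gone at 84.

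**4. How often the switch would occur.** Assume a denominator of 88 and independent completion, with X ~ Binomial(88, 1 − m), where m is the missing rate.

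| m | VAS stays primary, P(X ≥ 84) | P(80 ≤ X ≤ 83) | P(X < 80) | Share of switches with X ≥ 80 |
|---|---|---|---|---|
| 2% | 0.968 | 0.032 | 0.000 | 99.8% |
| 3% | 0.875 | 0.124 | 0.001 | 98.9% |
| 4% | 0.724 | 0.268 | 0.009 | 96.9% |
| 5% | 0.549 | 0.419 | 0.032 | 92.9% |
| 7% | 0.254 | 0.583 | 0.162 | 78.2% |
| 10% | 0.053 | 0.424 | 0.523 | 44.7% |

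**5. What can be said about power.** No VAS SD is stated, and the sample-size text speaks of change while the primary outcome is pain at 48 hours. Back-solving with SD = d × √(n / (2 × DE)) / (1.960 + 0.842):

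- d = 1.3, n = 40: SD 2.08 with DE = 1, or 1.58 with DE = 1 + 9 × 0.08 = 1.72.
- d = 1.8, n = 20: SD 2.03 with DE = 1, or 1.55 with DE = 1.72.

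The implied SD is about 1.5 to 2.1, depending on how clustering entered, so the 80% cannot be verified. For the MPQ-SF no power can be computed at all, because there is no score, SD or target difference.

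**The case against.** The rule is prespecified, is worded the same in both places, and is triggered by completion rather than by results. The fallback has a sensible purpose: a paper form may not come back, while a live questionnaire is captured on the call. A completeness limit can also reasonably be stricter than a power limit, since 80 of 88 scores may satisfy power and still leave 9% of an intention-to-treat population unobserved. And the rule may concern only patients who were reached and instructed, with the 10% reserve covering those never reached.

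Much of this stands. The denominator is open, so the 80-to-83 band is certain only at 88. The fallback does address diary loss, although patients not reached by telephone would lack the MPQ-SF as well. The objection does not supply the missing definition or the missing MPQ-SF score, and unspecified sensitivity analyses do not settle which result is primary.

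Three stronger readings are tempting but not supported:

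- **That 80 VAS scores always lose the VAS.** This depends on a denominator the plan does not state.
- **That the switch biases the comparison or inflates type I error.** The stated trigger is form completion, not the treatment difference.
- **That MPQ-SF scoring was never defined.** The plan notes "A telephone script is also included in this IRB application", and that script is not among the supplied documents.

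**Conclusion.** The concern holds in conditional form. The primary pain scale depends on an undefined compliance figure, and the fallback has no score, target difference or power in the supplied documents. If all 88 randomized are the denominator, 80 to 83 VAS scores meet the sample-size requirement and still make the VAS non-primary. If patients reached are the denominator, the conflict shrinks and disappears at 84 or fewer.

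The size depends on an assumed non-completion rate, with independent completion and a denominator of 88. A switch is unlikely at 2–3% missing (3–13%), close to even at 5% (45%), and near certain at 10% (95%). At 5% or below, about 93% or more of switches would occur with at least 80 VAS scores available.

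The switch alters the trial's conclusion only if the two scales disagree, and the documents do not say how likely that is. Nor can one say that an adequately powered VAS analysis is discarded, because the VAS SD is not given. This is a cheap improvement, not a threat to validity.

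**What to change.** In both the Day Two text and the Primary Outcome text:

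- Delete the 95% condition and the back-up sentence. Name the 48-hour VAS as the single primary outcome for all randomized patients, whatever the completion rate.
- Prespecify one method for missing VAS scores using data already collected. One option is multiple imputation with arm, baseline VAS and MPQ-SF, and the 48-hour MPQ-SF where available.
- Report VAS completion by arm, out of all randomized.
- Report the MPQ-SF, with a named score, as a secondary or sensitivity outcome.

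The cost is wording only, with no new data. The downside is more reliance on missing-data assumptions if diary completion is poor, especially for patients who also miss the call and so have no 48-hour MPQ-SF.

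A smaller repair would define compliance and its denominator, assess it pooled and blinded, and name the MPQ-SF score. That removes the ambiguity. Counted over all randomized, it still makes the VAS non-primary at 80 to 83 scores; counted over patients reached, it largely removes that band. In both cases the fallback stays unsized. Neither repair supplies the missing VAS SD, which has to be stated separately before the 80% power can be checked.
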